6.5.1 Rescue Medications and Supportive Care

Participants should receive appropriate supportive care measures as deemed necessary by the treating investigator. Suggested supportive care measures for the management of AEs with potential immunologic etiology are outlined along with the dose modification guidelines in Section 6.6, Table 4. Where appropriate, these guidelines include the use of oral or IV treatment with corticosteroids, as well as additional anti-inflammatory agents if symptoms do not improve with administration of corticosteroids. Note that several courses of steroid tapering may be necessary as symptoms may worsen when the steroid dose is decreased. For each disorder, attempts should be made to rule out other causes such as metastatic disease or bacterial or viral infection, which might require additional supportive care. The treatment guidelines are intended to be applied when the investigator determines the events to be related to pembrolizumab.

Note: If after the evaluation of the event, it is determined not to be related to pembrolizumab, the investigator does not need to follow the treatment guidance. Refer to Table 4 in Section 6.6 for guidelines regarding dose modification and supportive care.

It may be necessary to perform conditional procedures such as bronchoscopy, endoscopy, or skin photography as part of evaluation of the event.

6.6 Dose Modification (Escalation/Titration/Other)

Pembrolizumab dose reductions are not permitted. Pembrolizumab treatment may be interrupted or discontinued due to toxicity. Pembrolizumab may be interrupted for a maximum of 12 weeks. An interruption of study intervention for more than 12 weeks will require Sponsor approval before treatment can be resumed (see Section 6.4). See Appendix 7 for country-specific dose modification requirements.

If radiotherapy is not completed for any reason, the participant may continue with pembrolizumab/placebo for up to 17 total treatment cycles (1 year). If SBRT is interrupted due to toxicity, all fractions of radiotherapy must be completed prior to Cycle 2 Day 1 of pembrolizumab/placebo (day second dose is administered) or SBRT must be discontinued early. Should the participant develop radiation pneumonitis, refer to Table 4 to follow the same management guidelines for irAE pneumonitis, specifically with action taken for study intervention, and treat as per local SOC.

Dose Modification and Toxicity Management for Immune-related AEs Associated With Pembrolizumab

AEs associated with pembrolizumab exposure may represent an immune-related response. These irAEs may occur shortly after the first dose or several months after the last dose of pembrolizumab treatment and may affect more than one body system simultaneously. Therefore, early recognition and initiation of treatment is critical to reduce complications. Based on existing clinical study data, most irAEs were reversible and could be managed with interruptions of pembrolizumab, administration of corticosteroids, and/or other supportive care. For suspected irAEs, ensure adequate evaluation to confirm etiology or exclude other causes. Additional procedures or tests such as bronchoscopy, endoscopy, skin biopsy may be included as part of the evaluation.

Based on the severity of irAEs, withhold or permanently discontinue pembrolizumab and administer corticosteroids.

Dose Modification and Toxicity Management Guidelines for irAEs Associated With Pembrolizumab Monotherapy, Coformulations, or IO Combinations are provided in Table 4.

Table 4Dose Modification and Toxicity Management Guidelines for Immune-relatedAdverse Events Associated with Pembrolizumab Monotherapy, Coformulations or IOCombinations

General instructions:

- 1. Severe and life-threatening irAEs should be treated with IV corticosteroids followed by oral steroids. Other immunosuppressive treatment should begin if the irAEs are not controlled by corticosteroids.
- 2. Pembrolizumab monotherapy, coformulations or IO combinations must be permanently discontinued if the irAE does not resolve or the corticosteroid dose is not ≤10 mg/day within 12 weeks of the last treatment.
- 3. The corticosteroid taper should begin when the irAE is \leq Grade 1 and continue at least 4 weeks.
- 4. If pembrolizumab monotherapy, coformulations or IO combinations have been withheld, treatment may resume after the irAE decreased to \leq Grade 1 after corticosteroid taper.

irAEs	Toxicity Grade (CTCAE v4.0)	Action With Pembrolizumab Monotherapy, Coformulations or IO Combinations	Corticosteroid and/or Other Therapies	Monitoring and Follow-up
Pneumonitis	Grade 2	Withhold	• Administer corticosteroids (initial dose of 1-2	• Monitor participants for signs and symptoms of
	Recurrent Grade 2 or Grade 3 or 4	Permanently discontinue	mg/kg prednisone or equivalent) followed by taper	 Evaluate participants with suspected pneumonitis with radiographic imaging and initiate corticosteroid treatment
				 Add prophylactic antibiotics for opportunistic infections

irAEs	Toxicity Grade (CTCAE v4.0)	Action With Pembrolizumab Monotherapy, Coformulations or IO Combinations	Corticosteroid and/or Other Therapies	Monitoring and Follow-up
Diarrhea / Colitis	Grade 2 or 3	Withhold	• Administer corticosteroids (initial dose of 1-2 mg/kg prednisone or equivalent) followed by taper	• Monitor participants for signs and symptoms of enterocolitis (ie, diarrhea, abdominal pain, blood or mucus
	Recurrent Grade 3 or Grade 4	Permanently discontinue		in stool with or without fever) and of bowel perforation (ie, peritoneal signs and ileus)
				• Participants with ≥Grade 2 diarrhea suspecting colitis should consider GI consultation and performing endoscopy to rule out colitis
				 Participants with diarrhea/colitis should be advised to drink liberal quantities of clear fluids. If sufficient oral fluid intake is not feasible, fluid and electrolytes should be substituted via IV infusion.
AST / ALT Elevation or Increased Bilirubin	Grade 2	Withhold	 Administer corticosteroids (initial dose of 0.5- 1 mg/kg prednisone or equivalent) followed by taper 	 Monitor with liver function tests (consider weekly or more frequently until liver enzyme value returned to baseline or is stable)
	Grade 3 or 4	Permanently discontinue	 Administer corticosteroids (initial dose of 1-2 mg/kg prednisone or equivalent) followed by taper 	

irAEs	Toxicity Grade (CTCAE v4.0)	Action With Pembrolizumab Monotherapy, Coformulations or IO Combinations	Corticosteroid and/or Other Therapies	Monitoring and Follow-up
T1DM or Hyperglycemia	New onset T1DM or Grade 3 or 4 hyperglycemia associated with evidence of β -cell failure	Withhold ^a	 Initiate insulin replacement therapy for participants with T1DM Administer anti- hyperglycemic in participants with hyperglycemia 	 Monitor participants for hyperglycemia or other signs and symptoms of diabetes
Hypophysitis	Grade 2 Grade 3 or 4	Withhold or permanently discontinue ^a	 Administer corticosteroids and initiate hormonal replacements as clinically indicated 	 Monitor for signs and symptoms of hypophysitis (including hypopituitarism and adrenal insufficiency)
Hyperthyroidism	Grade 2 Grade 3 or 4	Continue Withhold or Permanently discontinue ^a	• Treat with non- selective beta- blockers (eg, propranolol) or thionamides as appropriate	 Monitor for signs and symptoms of thyroid disorders
Hypothyroidism	Grade 2-4	Continue	 Initiate thyroid replacement hormones (eg, levothyroxine or liothyronine) per standard of care 	 Monitor for signs and symptoms of thyroid disorders
Nephritis and	Grade 2	Withhold	• Administer	• Monitor changes of
renal dysfunction	Grade 3 or 4	Permanently discontinue	corticosteroids (prednisone 1-2 mg/kg or equivalent) followed by taper	renal function
Myocarditis	Grade 1	Withhold	• Based on severity	• Ensure adequate
	Grade 2, 3 or 4	Permanently discontinue	of AE administer corticosteroids	evaluation to confirm etiology and/or exclude other causes

irAEs	Toxicity Grade (CTCAE v4.0)	Action With Pembrolizumab Monotherapy, Coformulations or IO Combinations	Corticosteroid and/or Other Therapies	Monitoring and Follow-up
All Other irAEs	Persistent Grade 2	Withhold	 Based on severity of AE administer 	• Ensure adequate evaluation to confirm
	Grade 3	Withhold or discontinue ^b	corticosteroids	etiology or exclude other causes
	Recurrent Grade 3 or Grade 4	Permanently discontinue		

AE(s)=adverse event(s); ALT= alanine aminotransferase; AST=aspartate aminotransferase; CTCAE=Common Terminology Criteria for Adverse Events; DRESS=Drug Rash with Eosinophilia and Systemic Symptom; GI=gastrointestinal; IO=immuno-oncology; ir=immune related; IV=intravenous; SJS=Stevens-Johnson Syndrome; T1DM=type 1 diabetes mellitus; TEN=Toxic Epidermal Necrolvsis; ULN=upper limit of normal.

Note: Non-irAE will be managed as appropriate, following clinical practice recommendations.

^a The decision to withhold or permanently discontinue pembrolizumab monotherapy, coformulations or IO combinations is at the discretion of the investigator or treating physician. If control achieved or ≤ Grade 2, pembrolizumab monotherapy, coformulations or IO combinations may be resumed.

^b Events that require discontinuation include, but are not limited to: Guillain-Barre Syndrome, encephalitis, myelitis, DRESS, SJS, TEN and other clinically important irAEs (eg, vasculitis and sclerosing cholangitis).

Dose Modification and Toxicity Management of Infusion Reactions Related to Pembrolizumab

Pembrolizumab may cause severe or life-threatening infusion reactions including severe hypersensitivity or anaphylaxis. Signs and symptoms usually develop during or shortly after drug infusion and generally resolve completely within 24 hours of completion of infusion. Dose modification and toxicity management guidelines on pembrolizumab associated infusion reaction are provided in Table 5.

NCI CTCAE Grade	Treatment	Premedication at Subsequent Dosing
Grade 1 Mild reaction; infusion interruption not indicated; intervention not indicated	Increase monitoring of vital signs as medically indicated until the participant is deemed medically stable in the opinion of the investigator.	None
Grade 2 Requires therapy or infusion interruption but responds promptly to symptomatic treatment (eg, antihistamines, NSAIDs, narcotics, IV fluids); prophylactic medications indicated for ≤24 hours	Stop Infusion.Additional appropriate medical therapy may include but is not limited to:IV fluidsAntihistaminesNSAIDsAcetaminophenNarcoticsIncrease monitoring of vital signs as medically indicated until the participant is deemed medically stable in the opinion of the investigator.If symptoms resolve within 1 hour of stopping drug infusion, the infusion may be restarted at 50% of the original infusion rate (eg, from 100 mL/hr to 50 mL/hr). Otherwise, dosing will be held until symptoms resolve and the participant should be premedicated for the next scheduled dose.Participants who develop Grade 2 toxicity despite adequate premedication should be permanently discontinued from further study drug intervention.	Participant may be premedicated 1.5 h (± 30 minutes) prior to infusion of study intervention with: Diphenhydramine 50 mg po (or equivalent dose of antihistamine). Acetaminophen 500-1000 mg po (or equivalent dose of analgesic).
Grades 3 or 4 Grade 3: Prolonged (ie, not rapidly responsive to symptomatic medication and/or brief interruption of infusion); recurrence of symptoms following initial improvement; hospitalization indicated for other clinical sequelae (eg, renal impairment, pulmonary infiltrates) Grade 4: Life-threatening; pressor or ventilatory support indicated	Stop Infusion. Additional appropriate medical therapy may include but is not limited to: Epinephrine** IV fluids Antihistamines NSAIDs Acetaminophen Narcotics Oxygen Pressors Corticosteroids Increase monitoring of vital signs as medically indicated until the participant is deemed medically stable in the opinion of the investigator. Hospitalization may be indicated. **In cases of anaphylaxis, epinephrine should be used immediately. Participant is permanently discontinued from further study drug intervention.	No subsequent dosing

Table 5Pembrolizumab Infusion Reaction Dose Modification and Treatment
Guidelines

NCI CTCAE Grade	Treatment	Premedication at Subsequent Dosing
CTCAE = Common Terminology Criteria for Adverse Event; IV = intravenous; NCI = National Cancer Institute;		
NSAID = nonsteroidal anti-inflammatory drug; po = orally.		
Appropriate resuscitation equipment should be available at the bedside and a physician readily available during the		
period of drug administration.		
For further information, please refer to the Common Terminology Criteria for Adverse Events v4.0 (CTCAE) at		
http://ctep.cancer.gov		

Other Allowed Dose Interruption for Pembrolizumab

Pembrolizumab may be interrupted for situations other than treatment-related AEs such as medical / surgical events or logistical reasons not related to study therapy. Participants should be placed back on study therapy within 3 weeks of the scheduled interruption, unless otherwise discussed with the Sponsor. The reason for interruption should be documented in the participant's study record.

6.7 Intervention After the End of the Study

There is no study-specified intervention following the end of the study.

6.8 Clinical Supplies Disclosure

The pembrolizumab treatment in the study is blinded but supplies are provided open label; therefore, unblinded pharmacist or qualified trial site personnel will be used to blind supplies. Study intervention identity (name, strength, or potency) is included in the label text; random code/disclosure envelopes or lists are not provided.

6.9 Standard Policies

Study site personnel will have access to a central electronic treatment allocation/randomization system (IVRS/IWRS system) to allocate participants, to assign study intervention to participants, and to manage the distribution of clinical supplies. Each person accessing the IVRS system must be assigned an individual unique PIN. They must use only their assigned PIN to access the system, and they must not share their assigned PIN with anyone.

6.9.1 Study Site Retention Samples

The investigator is responsible for keeping accurate records of the clinical supplies received from the Sponsor or designee, the amount dispensed to the participants, and the amount remaining at the conclusion of the study. For all study sites, the local country Sponsor personnel or designee will provide appropriate documentation that must be completed for drug accountability and return, or local discard and destruction if appropriate. Where local discard and destruction is appropriate, the investigator is responsible for ensuring that a local discard/destruction procedure is documented.

Clinical supplies must be stored in a secure, limited access location under the storage conditions specified on the label.

Receipt and dispensing of study medication must be recorded by an authorized person at the study site.

Clinical supplies may not be used for any purpose other than that stated in the protocol.

7 DISCONTINUATION OF STUDY INTERVENTION AND PARTICIPANT WITHDRAWAL

7.1 Discontinuation of Study Intervention

NOTE: Based on the data from an interim safety and efficacy analysis for KEYNOTE¬867 (data cutoff 11-JUN-2024), the eDMC recommended stopping the study since pembrolizumab in combination with SBRT did not demonstrate an improvement in EFS or OS, the study's primary endpoint and key secondary endpoint, respectively, compared to placebo plus SBRT, and the benefit/risk profile of the combination did not support continuing the trial. All prespecified interim analyses after IA1 and final analysis of the study described in the SAP will not be performed. Safety analysis will be performed at the end of the study; there will be no further pre-planned analyses for efficacy and ePRO endpoints collected from participants beyond the IA1 cutoff date of 11-JUN-2024. The subsections below are retained for reference.

Discontinuation of study intervention does not represent withdrawal from the study.

As certain data on clinical events beyond study intervention discontinuation may be important to the study, they must be collected through the participant's last scheduled followup, even if the participant has discontinued study intervention. Therefore, all participants who discontinue study intervention prior to completion of the protocol-specified treatment period regimen will still continue to participate in the study as specified in Section 1.3 and Section 8.11.3.

Participants may discontinue study intervention at any time for any reason or be dropped from the study intervention at the discretion of the investigator should any untoward effect occur. In addition, a participant may be discontinued from study intervention by the investigator or the Sponsor if study intervention is inappropriate, the study plan is violated, or for administrative and/or other safety reasons. Specific details regarding procedures to be performed at study intervention discontinuation are provided in Section 8.1.9.

A participant must be discontinued from study intervention, but continue to be monitored in the study for any of the following reasons:

- The participant or participant's legally acceptable representative requests to discontinue study intervention.
- The participant interrupts study intervention administration for more than 12 weeks without Sponsor Approval.
- The participant does not start SBRT for any reason.
- The participant's treatment assignment has been intentionally unblinded by the investigator, MSD subsidiary, or through the emergency unblinding call center. Note: if a participant's treatment is unintentionally unblinded, the participant is not required to discontinue treatment.

- Any prolonged interruption of study intervention beyond the permitted periods, for irAE management or other allowed dose interruptions, as noted in Section 6.6, require Sponsor consultation prior to restarting treatment. If treatment will not be restarted, the participant will continue to be monitored in the study and the reason for discontinuation of study intervention will be recorded in the medical record.
- The participant has a medical condition or personal circumstance which, in the opinion of the investigator and/or Sponsor, places the participant at unnecessary risk from continued administration of study intervention.
- Pathological recurrence of disease or radiographic recurrence of disease outlined in Section 8.2.1.3. If the radiographic recurrence is biopsied and the pathology is negative, the patient may continue treatment until pathological or radiographic confirmation of recurrence by repeat imaging or biopsy.
- The participant has a confirmed positive serum pregnancy test.
- Completion of 17 doses (approximately 1 year) of pembrolizumab/placebo.
- Prohibited concomitant therapy or vaccinations as defined in Section 6.5 are administered during the study.
- Recurrent Grade 2, Grade 3, or Grade 4 pneumonitis of any cause and Grade 3 colitis.
- Any progression or recurrence of any malignancy, or any occurrence of another malignancy that requires active treatment.
- Any study intervention-related toxicity specified as a reason for permanent discontinuation as defined in the guidelines for dose modification due to AEs in Section 6.6.

For participants who are discontinued from study intervention but continue to be monitored in the study, all visits and procedures, as outlined in the SoA, should be completed. Participants who discontinue treatment for reasons other than pathologically confirmed recurrence of disease (ie, by biopsy), should continue to be monitored by tumor imaging until BICR-verified disease recurrence as described in Section 8.2.1.4, withdrawing consent, pregnancy, death, or loss to follow-up, whichever occurs first. Participants assigned to placebo will not have an opportunity to crossover to pembrolizumab at the time of recurrence within the scope of this clinical trial; however, pembrolizumab may be administered as a subsequent therapy off-study based on the current pembrolizumab product labeling if indicated for that participant's disease state at the time of recurrence or at any point in the course of the disease.

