NOTE: IF A RECHALLENGE IS PLANNED FOR AN AE THAT WAS SERIOUS AND MAY HAVE BEEN CAUSED BY THE STUDY INTERVENTION, OR IF REEXPOSURE TO THE STUDY INTERVENTION POSES ADDITIONAL POTENTIAL SIGNIFICANT RISK TO THE PARTICIPANT THEN THE RECHALLENGE MUST BE APPROVED IN ADVANCE BY THE SPONSOR CLINICAL DIRECTOR AS PER DOSE MODIFICATION GUIDELINES IN THE PROTOCOL, AND IF REQUIRED, THE IRB/IEC.

- **Consistency with study intervention profile:** Is the clinical/pathological presentation of the AE consistent with previous knowledge regarding the study intervention or drug class pharmacology or toxicology?
- The assessment of relationship will be reported on the case report forms/worksheets by an investigator who is a qualified physician according to their best clinical judgment, including consideration of the above elements.

- Use the following scale of criteria as guidance (not all criteria must be present to be indicative of a study intervention relationship).
 - Yes, there is a reasonable possibility of study intervention relationship:
 - There is evidence of exposure to the study intervention. The temporal sequence of the AE onset relative to the administration of the study intervention is reasonable. The AE is more likely explained by the study intervention than by another cause.
 - No, there is not a reasonable possibility of study intervention relationship:
 - Participant did not receive the study intervention OR temporal sequence of the AE onset relative to administration of the study intervention is not reasonable OR the AE is more likely explained by another cause than the study intervention. (Also entered for a participant with overdose without an associated AE.)
- The investigator must review and provide an assessment of causality for each AE/SAE and document this in the medical notes.
- There may be situations in which an SAE has occurred and the investigator has minimal information to include in the initial report to the Sponsor. However, it is very important that the investigator always make an assessment of causality for every event before the initial transmission of the SAE data to the Sponsor.
- The investigator may change their opinion of causality in light of follow-up information and send an SAE follow-up report with the updated causality assessment.
- The causality assessment is 1 of the criteria used when determining regulatory reporting requirements.

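### Do Section 7.1 and Table 4 disagree on a first Grade 3 colitis in a way that calls for a change?

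*Combined protocol and SAP*

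**What the plan says.** Section 7.1 opens its list with the sentence "A participant must be discontinued from study intervention, but continue to be monitored in the study for any of the following reasons". One bullet reads "Recurrent Grade 2, Grade 3, or Grade 4 pneumonitis of any cause and Grade 3 colitis". The last bullet adds any intervention-related toxicity for which Section 6.6 specifies permanent discontinuation. The Amendment 08 note at the head of Section 7.1 ends "The subsections below are retained for reference".

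In Section 6.6, the diarrhea/colitis row of Table 4 says to withhold for Grade 2 or 3, and to discontinue permanently for "Recurrent Grade 3 or Grade 4". General instruction 4 of the table begins "If pembrolizumab monotherapy, coformulations or IO combinations have been withheld, treatment may resume after the irAE decreased to" and goes on to Grade 1 or lower after the corticosteroid taper. The row covers diarrhea as well as colitis: its monitoring column says that participants with Grade 2 or worse diarrhea and suspected colitis "should consider GI consultation and performing endoscopy to rule out colitis".

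Section 6.5.1 limits the reach of the table: "The treatment guidelines are intended to be applied when the investigator determines the events to be related to pembrolizumab". Section 10.3.5 adds, for a serious event possibly caused by study intervention, or where re-exposure carries significant additional risk, that "THE RECHALLENGE MUST BE APPROVED IN ADVANCE BY THE SPONSOR CLINICAL DIRECTOR AS PER DOSE MODIFICATION GUIDELINES IN THE PROTOCOL".

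**The concern.** Two current parts of one protocol seem to give different answers for the same patient. Section 7.1 attaches no recurrence condition to Grade 3 colitis, whereas Table 4 lets treatment restart after a first episode. Neither says which takes precedence.

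While dosing was open, one site could have stopped treatment and another restarted it, each able to cite the protocol. Discontinuations due to AEs are a secondary safety endpoint (Section 3), and exposure is summarised in cycles received (Section 9.12), so uneven practice could have left a mark on both. One task is also still open. Section 9.11 promises a report of deviations from protocol-directed administration, and Section 9.2 wants deviations identified before the final database is unblinded. Whether a resumption counts as a deviation depends on which text is applied. Section 6.1 lets investigators apply for unblinding in the meantime, so a late choice could be made with some treatment assignments known.

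**Working it through.** There is no planned figure to reproduce, so the check compares the texts and then follows the consequences.

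**Where the texts differ**

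| Case | Section 7.1, natural reading | Table 4 | Conflict? |
|---|---|---|---|
| First Grade 3 colitis, related, withheld and not resumed | discontinue | withhold; resumption optional | No |
| First Grade 3 colitis, related, withheld then resumed | discontinue | resumption permitted | **Yes** |
| First Grade 3 diarrhea, colitis ruled out | colitis bullet not triggered | withhold; resumption optional | No |
| First Grade 3 colitis, not related | discontinue | guidance need not be followed (Section 6.5.1) | No |
| Recurrent Grade 3, or Grade 4, related | discontinue (last bullet) | discontinue permanently | No |

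Only the second row conflicts, and it sets a permission against a requirement. No site was ever told to do two incompatible things.

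**Whether another text settles it**

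- *The last bullet of Section 7.1* adds the Section 6.6 triggers. It does not qualify the colitis bullet.
- *Footnote a of Table 4* gives the investigator discretion, but it is attached to the diabetes, hypophysitis and hyperthyroidism rows, not to colitis.
- *The rechallenge note in Section 10.3.5* requires prior Sponsor approval, given under the dose modification guidelines. An approved restart could still be contrary to Section 7.1.
- *Reading the word recurrent across the whole bullet* brings the colitis wording into line with Table 4. A first related Grade 3 or 4 pneumonitis would then drop out of this bullet, but the last bullet brings it back through Section 6.6. This removes the conflict, though the grammar is less natural. The bullet is therefore ambiguous as well as inconsistent with the table.

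**What the disagreement can still reach**

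1. *Dosing:* nothing. Section 6.1 has all participants stop pembrolizumab or placebo.
2. *Efficacy and PRO:* nothing further is planned on data beyond the IA1 cutoff (Section 9.6). The EFS rule in Section 9.6.1.1 counts events whether or not study drug was stopped.
3. *Analysis populations:* ITT, APaT and the PRO full analysis set (Sections 9.5.1 to 9.5.3) do not exclude anyone for a deviation, and there is no per-protocol set.
4. *Safety:* AE discontinuations and cycles are facts already recorded. Rewording either passage alters none of them.
5. *Deviation report:* a resumption after a first related Grade 3 colitis may or may not be listed.

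**Scale:** 436 / 2 = 218 per arm, and 1 / 218 = 0.46%. This is the share of an arm that one affected participant represents, assuming all randomized participants were dosed. It is not a planned statistic, since the SAP defines no deviation proportion by arm.

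**The case for a change.** The best case for acting is that both texts stand in the current protocol and the deviation report is still owed. Section 9.11, unlike the sections on statistical methods and interim analyses, carries no note that it is kept only for reference. Whether a resumption was a deviation cannot be answered without choosing a passage, and the choice is cleaner before treatment assignments are known. One recorded line would settle it at almost no cost.

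Much of this stands. The inconsistency is real on the natural reading, the classification question is open, and a choice made blind is better than one made later. It would also be too strong to say that only deviation labels were ever at stake. Sites could have followed either text while dosing continued, so AE discontinuations and exposure should be read with that in mind.

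It does not carry through to a change. Section 9.2 already places deviation identification before final unblinding, which is when the review team would meet such a case and note how it was handled. Data management procedures are provided separately (Section 10.1.8), so the criterion may already be written down; these documents cannot show either way. Serious, possibly related cases that restarted needed Sponsor approval and should be known to the Sponsor. Against this, editing Section 7.1 or Table 4 means another amendment to a stopped study, with ethics approval if the revision counts as significant (Section 10.1.1), and no result would move.

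**Conclusion.** No change to the plan follows, because there is nothing to gain. On its natural reading Section 7.1 is inconsistent with Table 4 for one narrow case: a first Grade 3 colitis, judged related to pembrolizumab, with dosing resumed. No future dose, recorded count, analysis population or specified analysis depends on it. What is left is the label on an unknown and possibly zero number of past cases in a deviation report, which the blinded deviation review can settle case by case, and a caution when interpreting AE discontinuations and cycles received.

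This rests on three points: dosing has ended as Section 6.1 states, no analysis excluding deviators is added later, and deviations are identified before final unblinding as Section 9.2 requires. As clinical text, the two passages would have to be reconciled by the clinical team before either guided dosing again. This review takes no view on which is right.
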